Description of Study Intervention:	Radiotracer production: Blue Earth Diagnostics Ltd, manufacturers of ¹⁸ F-rhPSMA-7.3, has pledged support with gratis radiotracer unit doses supplied from PET-NET Solutions, a commercial radiopharmacy who made similar unit doses under IND #141561 for the Phase 3 trial also completed at our center. This study IND #162587 is held by [name].
Study Duration:	5 years

1.4 1.2 Schema

1.5 1.3 Schedule of Assessments

Procedures	Enrollment/Screening (-30 days)	Study Visit 1 PET/CT 1 (Within 30 days of enrollment)	(Study Visit 2 PET/CT 2 (Within 2-7 days of Visit 1)	Follow up (1-3 business days after each PET/CT)
Informed consent	X			
Demographics	X			
Pertinent Medical history	X			
Administer study intervention		X	X	
AE assessment		X	X	X
Complete Case Report Forms (CRFs)	X	X	X	X

2. Objectives (and Endpoints)

OBJECTIVES	ENDPOINTS

Primary
 
1. To determine if administering 20 mg furosemide IV at the time of radiotracer injection significantly reduces bladder activity compared with the same patient scanned without furosemide as internal control
 
20 patients with biochemical recurrence of prostate cancer following radical prostatectomy will be sequentially assigned to either undergo 18F-rhPSMA-7.3 PET/CT without furosemide first followed by a second PET/CT with furosemide at 2-7 days afterward, or vis-versa (10 in each group). Patients will be encouraged to void during the uptake phase up to 15 minutes before being placed on the scanner for imaging. Bladder activity (SUVmax, SUVmean, and bladder volume), ureteral activity (SUVmax, SUVmean), as well as renal activity (SUVmax, SUVmean), will be recorded. The presence and degree of halo artifacts around the bladder and kidney will also be recorded. Exclusion criteria for this trial will include urinary incontinence that may interfere with performing the study and contraindications to furosemide. As always, patients will be encouraged to arrive well hydrated and to drink an additional 500-1000 ml of water during the uptake phase.
	Determine the difference in the urinary bladder activity on ¹⁸ F-rhPSMA-7.3 PET/CT with furosemide compared with ¹⁸ F-rhPSMA-7.3 PET/CT without furosemide in biochemical recurrence of prostate cancer post radical prostatectomy (Specific Aim 1).

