We hypothesize that the administration of intravenous furosemide at the time of radiotracer injection will reduce the activity of ¹⁸F-rhPSMA-7.3 in the urinary bladder and facilitates the identification of prostate bed recurrence in men with rising serum PSA post-prostatectomy. We also hypothesize that reduced urinary activity of ¹⁸F-rhPSMA-7.3 will improve readers' confidence in assessing prostate bed recurrence of prostate cancer. An improved lesion detection will influence management decisions.

To test these hypotheses with the highest scientific rigor, we propose a study including men with BCR post-prostatectomy. Each patient will undergo two sets of ¹⁸F-rhPSMA-7.3 PET/CT scans, one with and the other without furosemide, and the level of urinary bladder activity, the detection rate of prostate bed recurrence and other lesions, will be compared between the two scans. In this manner, each patient will serve as their own control. We expect that the results from this study may generate sufficient evidence that may affect the workflow of ¹⁸F-rhPSMA-7.3 PET/CT imaging of BCR of prostate cancer, especially after FDA approval for use in routine clinical care.

2.4 3.2 Clinical Experience

Our preliminary data support a key scientific premise that the intravenous administration of furosemide at the time of radiotracer injection leads to lower radiotracer concentration in the urinary bladder. This finding is supported by published studies in the literature showing that intravenous administration of furosemide at the time of ⁶⁸Ga-PSMA-11 administration causes a reduction in

bladder activity, improves detection of local prostate bed recurrence, and improves reader confidence. Study Intervention/Investigational Agent

2.5 4.1 Description

IV injection of 8 mCi (296 MBq) \pm 20% of rhPSMA-7.3 (18F) diluted up to 10 mL will be used for each of the two PET scans. This dose is based on dosimetry data obtained from published phase I study data [21], and the dose utilized in the approval phase III trial that was recently concluded [NCT04186845]. The study will be performed under IND #162587 held by [name].

2.6 4.2 Drug/Device Handling

- Radiotracer handling and administration: Each individual dose of radiotracer will be specifically ordered and delivered on the day of the study for the research subject and administered by authorized personnel per standard radiotracer administration protocol of the institution and division.

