We will image 20 patients with biochemical recurrence of prostate cancer post-prostatectomy for this study. Based on prior observation, we assume an SUV mean of 9.2 (SD=11.1) in those receiving 20mg furosemide IV at the time of radiotracer injection, and an SUV mean of 2.6 (SD=1.0) in those not receiving furosemide (White Paper Prepared for Syncona: Evaluation of 18F-rhPSMA7, Unpublished). Assuming a correlation between paired measurements of 0.5 which results in a standard deviation of change in SUV mean of approximately 10, we have 80% power to detect that change in SUV mean (9.2 vs. 2.6) with 20 patients, assuming a Type I error of 0.05, using a paired t-test. The sample size was calculated using PASS 2020 v20.0.3.

Populations for analyses

Efficacy set: All patients administered both 20mg furosemide IV at the time of radiotracer injection and without furosemide.

Safety set: All patients receive a dose of the radiotracer with each study.

Statistical analyses:

General Approach

Continuous variables will be summarized using mean, median, interquartile range, standard deviation, and min/max. Categorical variables will be summarized using frequencies and percentages. All tests will be two-sided with an alpha level of 0.05, unless otherwise noted. Testing assumptions will be

assessed and verified. Statistical analysis will be conducted using SAS 9.4 (SAS Institute Inc., Cary, NC).

Analysis of the Primary Efficacy Endpoint

Change in bladder SUV mean: The primary endpoint is change in bladder activity, as measured by bladder SUV mean, between administration of 20mg furosemide IV at the time of radiotracer injection and without furosemide. Change in bladder SUV mean will be assessed using a paired t-test, or using a non-parametric equivalent such as a Wilcoxon signed rank test. Descriptively, change in bladder SUV mean will be reported for those administered 20mg furosemide IV at the time of radiotracer injection first (Group A), and those administered 20mg furosemide IV at the time of radiotracer injection second (Group B).

Analysis of the Secondary Endpoints:

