Bladder and renal activity: Change in bladder and renal activity, as measured by bladder SUV max, bladder volume, and renal SUV mean/max, between administration of 20mg furosemide IV at the time of radiotracer injection and without furosemide will be assessed using paired t-tests, or using non-parametric equivalents such as a Wilcoxon signed rank tests. Descriptively, bladder and renal activity will be reported for those administered 20mg furosemide IV at the time of radiotracer injection first (Group A), and those administered 20mg furosemide IV at the time of radiotracer injection second (Group B).

Recurrent disease rate: Recurrent disease is defined as presence of unequivocal soft tissue radiotracer uptake that is characteristic of malignancy in the prostate bed and/or surrounding soft tissues and within pelvic lymph nodes. Recurrent disease rates will be compared (furosemide vs. non-furosemide 18F-rhPSMA-7.3 PET scans using McNemar's tests. Rates will be reported, along with 95% exact confidence intervals using the Clopper-Pearson method. Descriptively, recurrent disease rate will be reported for those administered 20mg furosemide IV at the time of radiotracer injection first (Group A), and those administered 20mg furosemide IV at the time of radiotracer injection second (Group B).

Confidence score: The readers' confidence in identifying prostate bed, pelvic and retroperitoneal nodal disease and other recurrence on 18F-rhPSMA-7.3 PET/CT with furosemide compared with the 18F-rhPSMA-7.3 PET/CT without furosemide will be scored using a 5-point Likert scale. This analysis will be descriptive, with summary statistics reported with and without furosemide.

Safety Analyses: Not applicable.

Baseline Descriptive Statistics

Patient characteristics will be summarized descriptively, using mean, median, interquartile range, min/max, and standard deviation for continuous variables, and using frequencies and percentages for categorical variables.

Interim Analysis: N/A

16.2 Data/specimens:

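### Does the primary endpoint need a named effect estimate, a confidence interval and an explicit rule for choosing between the paired t-test and Wilcoxon?

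*Combined protocol and SAP*

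**What the plan says.** Section 2 (Objectives and Endpoints) words the primary endpoint as: "Determine the difference in the urinary bladder activity on" the scans with and without furosemide. Section 11.1 makes this the within-patient change in bladder SUVmean and gives the method: "Change in bladder SUV mean will be assessed using a paired t-test, or using a non-parametric equivalent such as a Wilcoxon signed rank test".

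The General Approach in 11.1 makes all tests two-sided at 0.05 "unless otherwise noted. Testing assumptions will be" assessed and verified. It summarises continuous variables by mean, median, interquartile range, SD and minimum/maximum. The primary analysis adds a breakdown by scan order: "Descriptively, change in bladder SUV mean will be reported for those administered 20mg furosemide IV" first or second.

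The other bladder and renal measures follow the same pattern; their changes "will be assessed using paired t-tests, or using non-parametric equivalents such as a Wilcoxon signed rank tests". The only interval named in 11.1 belongs to a secondary endpoint, recurrent disease: "Rates will be reported, along with 95% exact confidence intervals using the Clopper-Pearson method".

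**The concern.** An endpoint that is to determine a difference appears to have a test but no estimate, while a secondary endpoint gets exact 95% intervals. The two tests also lead to different quantities: the t-test goes with the mean change, and the signed-rank test with the Hodges-Lehmann shift. These agree for symmetric data, but the planning values (9.2 with SD 11.1 against 2.6 with SD 1.0) describe a positive variable whose SD exceeds its mean.

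The worry is that the reported size of the reduction could be picked after the data are seen. A t-interval for the mean could also be printed beside a Wilcoxon p-value and contradict it. Section 3.1 gives the size some weight: "We expect that the results from this study may generate sufficient evidence that may affect the workflow of" imaging with this tracer.

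**Working it through.** **1. The plan's own power figure.** Inputs from Sample size determination in 11.1: means 9.2 and 2.6, SDs 11.1 and 1.0, correlation 0.5, 20 patients, two-sided 0.05.

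- SD of change = √(11.1² + 1.0² − 2 × 0.5 × 11.1 × 1.0) = √113.11 = 10.64, which the plan rounds to 10.
- Noncentrality = (6.6/10) × √20 = 2.95 on 19 df, giving power of 79.9%. The stated 80% is reproduced. With SD 10.64 it is 74.9%.

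The trial is therefore sized on the mean difference with a paired t-test.

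**2. Is the skew real?** The Background section reports 17 pilot scans: mean 4.57, SD 6.4, range 1.4 to 28.8. Five without furosemide averaged 9.24 and twelve with it averaged 2.63.

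- Recombined mean: (5 × 9.24 + 12 × 2.63)/17 = 77.76/17 = 4.57. Using SDs 11.1 and 1.0, the recombined SD is 6.41. Both match.
- Largest value possible in the group of twelve: 2.63 + 11 × 1.0/√12 = 5.81. The 28.8 scan was therefore without furosemide.
- The other four average (46.2 − 28.8)/4 = 4.35, with implied SD √{[4 × 11.1² − (28.8 − 9.24)² − 4 × (4.35 − 9.24)²]/3} = 2.2.

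The skew is real in the pilot, and one scan carries most of it.

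**3. How far apart are the estimates?** Simulated trials of 20 pairs, log-scale correlation 0.5. SUVs are assumed lognormal apart from scans fixed at 28.8. Values are medians over trials, in SUV units.

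| Setting | Mean | Hodges-Lehmann (95% CI) | Median | Mean/median |
|---|---|---|---|---|
| Planning values | 6.3 | 4.5 (2.0–8.5) | 3.4 | 1.9 |
| Pilot-like, no scan at 28.8 | 1.7 | 1.5 (0.8–2.4) | 1.4 | 1.2 |
| One scan at 28.8 | 2.9 | 1.7 (0.9–2.9) | 1.5 | 1.9 |
| Two | 4.1 | 1.9 (0.9–3.6) | 1.6 | 2.6 |
| Four | 6.6 | 2.5 (1.2–13.5) | 1.9 | 3.5 |

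**4. Does the test decision suffer?** The plan names no normality test, so a 5% Shapiro-Wilk check on the differences was assumed. It leads to Wilcoxon in 92% of trials under planning values, 100% with one to four scans at 28.8, and 39% with none. Type I error is 4.5 to 5.2%. Power is at least 99.4% at correlation 0.5. With one scan at 28.8, Wilcoxon power is 97% at correlation 0.25, 93% at 0, and 82% at 0 with the remaining SD raised to 2.7.

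**5. How often could an interval contradict the test?** A t-interval including zero beside a significant Wilcoxon result occurs in 29% of trials with exactly one scan at 28.8, 10% with two, 4% under planning values, and under 0.5% with none, three or four. Weighting the one- and two-scan rates by binomial probabilities for 20 patients:

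- Rate 20%: 0.29 × 0.058 + 0.10 × 0.137 = 3%.
- Rate 10%: 0.29 × 0.270 + 0.10 × 0.285 = 11%.
- Rate 5%: 0.29 × 0.377 + 0.10 × 0.189 = 13%.

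The pilot rate of one in five has an exact 95% interval of 0.5 to 72%, so none of these can be preferred.

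**6. Can the interval be recovered from what is planned?** Yes, for the mean: half-width = 2.093 × SD/√20. With SD 10 this is 4.68, so a mean change of 6.6 would be read as 1.9 to 11.3.

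**The case for a change.** The best case for acting is that the gap is real and costs only a few sentences to close. No estimate is designated, the assumption check has no criterion, and under planning values it would usually lead to Wilcoxon, for which no companion estimate is named. The raw t-interval is also unreliable here: across ten simulated shapes it covered the mean in 74 to 95% of trials, while the Hodges-Lehmann interval covered its own target in 93.7 to 95.2%.

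The textual gap stands. The harm is weaker than it looks, for four reasons.

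- The contradiction requires pairing a t-interval with a Wilcoxon p-value, which the plan does not propose. An analyst who has left the t-test because its assumptions failed would not normally return to its interval.
- The two harms belong to different settings. The 3.5-fold gap needs four extreme scans, where contradiction is under 0.5%. The 29% contradiction needs exactly one, where the ratio is 1.9.
- Naming Wilcoxon with Hodges-Lehmann is not shown to be better. With four extreme scans its interval runs from 1.2 to 13.5, against 0.8 to 4.1 for the median, so the median would have to sit beside it. With the mean also reported, all three numbers would appear, as they can now.
- The objective stated at the head of 11.1 is whether furosemide significantly reduces bladder activity, which the test answers. The workflow sentence in 3.1 is only a hedged expectation.

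One further slip touches the direction of the change. Sample size determination says "we assume an SUV mean of 9.2 (SD=11.1) in those receiving 20mg furosemide IV at the time of radiotracer injection", whereas the Background attaches 9.24 to scans without furosemide. The two passages need reconciling as a clerical matter. Swapping the labels leaves the SD of change, the two-sided power and every analysis result as they were.

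**Conclusion.** The concern does not call for a change. Read plainly, 11.1 means a paired t-test unless its assumptions fail, then a rank-based test, with the mean and median change reported either way. That gives a sound test decision, and the missing estimate and interval are details an analyst would supply when reporting a paired comparison.

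What stays open is which figure leads the report. Under lognormal planning values the mean change is about 1.4 times the Hodges-Lehmann shift and 1.9 times the median. About 3.5 times the median arises only if four of 20 scans reach 28.8. These sizes rest on the lognormal assumption, a correlation of 0.5, and a pilot of five no-furosemide patients given rhPSMA-7 rather than rhPSMA-7.3, so the outlier pattern may not carry over. The conclusion on type I error also assumes that the assumption check is applied as described. An explicit estimate with its interval would be tidier reporting, but it would not alter the test, the sample size or the conclusion drawn from it.

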Histology proof of recurrence will not be required. All patients will be recruited from the radiation oncology unit and other oncology units under Emory Healthcare. All 20 patients will undergo two sets of 18F-rhPSMA-7.3 PET/CT scans, one with and the other without intravenous administration of 20 mg of furosemide at the time of radiotracer injection. All patients will have oral hydration with 500 to 1000 ml of water during the uptake phase. The first set of 10 patients will have a 18F-rhPSMA-7.3 PET/CT without-furosemide followed by a 18F-rhPSMA-7.3 PET/CT with-furosemide 2-7 days afterward. The second set of 10 patients will have their two 18F-rhPSMA-7.3

PET scans in the reverse order, with-furosemide first followed by without-furosemide 2-7 days afterward. Vital signs will be measured before and after each radiotracer administration. Each patient will undergo both imaging techniques, and the results will be interpreted blindly. A minimum of 2 days is required between the two 18F-rhPSMA-7.3 to allow for the complete decay of the radiotracer from the first scan before the second scan (physical half-life of 18F is 110 minutes). Patients will be allowed to void during the 60-70 minutes uptake period between 18F-rhPSMA-7.3 radiotracer administration and the commencement of PET/CT imaging. Patients will be encouraged to void at approximately 50 minutes post injection and encouraged to refrain from voiding 15 minutes before the commencement of the PET/CT (60-70 min post injection), if possible, to facilitate bladder distension.

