The study will be closed to recruitment once all 20 patients have been recruited, scanned with the 2 PET/CTs each and have completed follow-up (1-3 business days after each PET/CT). The study will be formally closed once all manuscripts have been published and all follow-up completed. There will be no other study-specific visits after the second PET/CT scan (visit 2), though the patient will be called by the study nurse within 1-3 business days after each study to ensure no delayed AEs occurred. The follow-up phone call for one study will be performed before the patient undergoes the subsequent scan.

3. Sharing of Results with Participants

PET findings will be used for research purposes within the context of the clinical trial as noted above. The key findings of the PET/CT and all incidental findings will be recorded in the clinical research form and emergent incidental findings will be communicated to the patient's physician who is also an investigator in this study. The non-emergent findings will be conveyed to the patient at the discretion of the patient's physician after a discussion of the risk versus benefit since this investigational radiotracer is not FDA approved for clinical use.

Incidental Findings

- a. All incidental findings noted by the imager will be discussed with the attending physician who is a co-investigator and documented in the electronic medical record.

Protocol Title: Strategy to Reduce Bladder Activity with rhPSMA 7.3: Comparison of 18F-rhPSMA 7.3 PET/CT with and without Furosemide in Biochemical Recurrence of Prostate Cancer

- b. The oncologist will educate the patient about the nature of the incidental finding, how to seek care from a clinician or specialist, obtaining health insurance to secure treatment, and/or referral to a clinical specialist, if one is required.
- c. Language to this effect is present in the consent form.

4. Study Timelines

The total duration of the study is 5 years, with an accrual rate of approximately 4 patients per year. For the individual study participant, the patient participation is complete after the 2nd PET/CT study. However, the participating patients may be followed up for correlation for up to 5 years after the study.

5. Inclusion and Exclusion Criteria

Adult patients with biochemical recurrence of prostate cancer, status post prostatectomy who meet the eligibility criteria will be enrolled in the study.

Inclusion Criteria

Adenocarcinoma of the prostate, post-prostatectomy.

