Biochemical recurrence of prostate cancer following RP with or without adjuvant or salvage therapy:
PSA ≥ 0.1 ng/mL

Age over 18.

Ability to provide written informed consent.

Patients with standard of care creatinine ≤ 1.3 mg/dL performed within 90 days prior to enrollment

Exclusion Criteria

Inability to undergo 18F-rhPSMA PET-CT, scontraindications to furosemide or urinary incontinence that may interfere with performing the study.

Population

(Y) 1. Adult patients with a diagnosis of adenocarcinoma of the prostate, post radical prostatectomy

(Y) 2. Biochemical recurrence as defined by PSA ≥ 0.1

(Y) 3. Age over 18 years and ability to give informed consent

(N) 4. Inability to undergo 18F-rhPSMA-7.3 PET/CT

(N) 5. Contraindications to furosemide such as true allergy or urinary incontinence that may interfere with performing the study

6. Local Number of Participants

All 20 patients will be recruited from Emory Healthcare

7. Recruitment Methods

All patients will be recruited from the radiation oncology unit and other oncology units such as medical oncology and urology under Emory Healthcare

8. Withdrawal of Participants

Anticipated withdrawal of patients is expected to be minimal in this small cohort of patients who will undergo a diagnostic PET/CT study. Anticipated causes include, unable to undergo PET/CT study due to issues with patient comfort such as severe claustrophobia. In case of early termination, the cause of the termination will be documented, and further imaging will not be performed. If for some reason a patient is unable to complete the second study after the first, this will be considered a withdrawal and another patient will be recruited in their place.

9. Risks to Participants

1. **Radiation Risks:** The principal risk associated with a radiation dose is the possibility of developing radiation-induced cancer later in life. However, the additional risk of radiation-induced cancer from these diagnostic procedures is low compared to the risks from the disease itself.
Human dosimetry data for ¹⁸F-rhPSMA-7.3 from the phase I study of Tolvanen and co-workers[18]: The (radiation absorbed) effective dose from the administration of 225 MBq of ¹⁸F-rhPSMA-7.3 is 0.0138 mSv/MBq at a 1-hour voiding interval. The organs with the highest absorbed radiation dose are the adrenals (0.184 mGy/MBq), the kidneys (0.172 mGy/MBq), and the submandibular glands (0.148 mGy/MBq).
The effective dose from the CT component of the study is 15.7mSv.

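### The primary test pools the changes from both scan orders and leaves order out: unbiased at the planned 10/10 with slightly reduced power under a visit effect, and biased only if the order groups end up unequal

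*Combined protocol and SAP*

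**What the plan says.** Section 2 (Objectives and Endpoints) assigns men sequentially to the scan without furosemide first and then with it, "or vis-versa (10 in each group". The Overall Design text in section 5.7 makes this a block assignment: the first ten men have the scan without furosemide first, and the last ten have the opposite order ("The second set of 10 patients will have their two" scans reversed).

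Section 11.1 sets the size: "We will image 20 patients with biochemical recurrence of prostate cancer post-prostatectomy for this study". Its primary analysis is: "Change in bladder SUV mean will be assessed using a paired t-test, or using a non-parametric equivalent such as a Wilcoxon signed rank test". Order then appears only as a summary: "Descriptively, change in bladder SUV mean will be reported for those administered 20mg furosemide IV", split into Group A (furosemide first) and Group B (furosemide second). The plan for bladder SUVmax, bladder volume and renal SUV has the same form. No term for scan position or sequence is planned.

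Two other statements bear on whether the groups stay equal. Section 4 (Study Timelines) says: "The total duration of the study is 5 years, with an accrual rate of approximately 4 patients per year". Section 8 (Withdrawal of Participants) says of a man who misses his second scan: "this will be considered a withdrawal and another patient will be recruited in their place". It does not say which order the replacement gets.

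**The concern.** This is a two-period, two-order crossover. Counterbalancing the order protects against a visit effect, but the planned test does not use it. Bladder SUVmean depends on urine volume and voiding. Oral intake may range from 500 to 1000 mL, and voiding is encouraged rather than fixed, so behaviour could differ between visits. The minimum of two days between scans is justified by tracer decay, which limits carryover but not a visit effect.

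A visit effect moves the change up in one order group and down by the same amount in the other. A one-sample test reads that separation as random variation. If the groups are unequal, the two shifts no longer cancel. Because the furosemide-first men are enrolled last, any shortfall would fall on that order. A drop in activity at the second visit would then be partly credited to furosemide.

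**Working it through.** **Inputs from 11.1.** Condition means 9.2 and 2.6 (difference 6.6), SDs 11.1 and 1.0, correlation 0.5, n = 20, two-sided alpha 0.05. Section 11.1 and the Background attach the two means to opposite conditions. That is a separate matter, and the calculations below do not depend on it.

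**The plan's own figure.** With the stated SD of change of about 10, the noncentral t (19 df, noncentrality 6.6/(10/√20)) gives 79.9%, so the stated 80% reproduces. The inputs themselves give SD = √(11.1² + 1.0² - 2×0.5×11.1×1.0) = 10.64 and power 74.9%. That gap is due to rounding and not to scan order. I use 10.64 below.

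**Model.** Let d be the value without furosemide minus the value with it, τ the furosemide effect and p the shift from visit 1 to visit 2. Then d averages τ + p in Group A and τ - p in Group B.

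- Pooled estimate: bias = p(nA - nB)/(nA + nB).
- Pooled variance at 10/10: expected value 10.64² + p²×20/19.
- Order-adjusted estimate: (mean of A + mean of B)/2, with SE = (SD/2)√(1/nA + 1/nB) on nA + nB - 2 df. It is unbiased at any split.

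**Planned 10/10.** The values of p are assumptions.

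| p (SUV) | Pooled SD | Pooled SE | Power, planned test | Power, order-adjusted |
|---|---|---|---|---|
| 0 | 10.64 | 2.38 | 74.9% | 74.7% |
| 1 | 10.68 | 2.39 | 74.6% | 74.7% |
| 2 | 10.83 | 2.42 | 73.4% | 74.7% |
| 3 | 11.07 | 2.48 | 71.5% | 74.7% |

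Simulated type I error of the planned test at 10/10 is about 4.6% at p = 2 and 4.2% at p = 3, so it is conservative.

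**Unequal groups.** Power is shown with no visit effect. Type I error is simulated on the plan's scale, with 60,000 or more trials per setting.

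| Order groups | Size of bias | Power, pooled | Power, adjusted | Pooled type I error, p = 1 / 2 / 3 |
|---|---|---|---|---|
| 10/7 | 3/17 = 0.18p | 67.1% | 65.4% | 4.9 / 4.8 / 4.6% |
| 10/5 | 5/15 = 0.33p | 60.9% | 55.5% | 5.1 / 5.3 / 5.5% |
| 10/3 | 7/13 = 0.54p | 53.9% | 40.6% | 5.2 / 6.0 / 7.1% |

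A 14/6 split among 20 men behaves much like 10/3: 5.3, 5.9 and 6.8%. The adjusted test stays at about 5% in every setting.

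**The case against.** The strongest case for leaving the plan alone has four parts.

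- **Balance is designed in.** Ten per order is stated, recruitment closes only once all 20 men have completed both scans and follow-up, and withdrawn men are replaced. Filling the vacated order is the natural reading. This stands as a reason to expect no bias, but the replacement's order is not written down.
- **The visit effect is hypothetical.** Hydration, voiding and uptake instructions are the same for both scans, 2 to 7 days apart. Nothing in the documents points to a systematic difference. A uniform drop of 3 SUV or more would also push the lower condition mean of 2.6 below zero, which an SUV cannot be. This stands for drops. With p at 1 or 2, the adjusted test gains only about 0.1 to 1.3 points of power.
- **Order is reported by group.** A large visit effect would be visible. That is true, but a descriptive split corrects neither the estimate nor the p-value, and an adjustment chosen after seeing the data would be post hoc.
- **Adjustment is not free when groups are unequal.** With no visit effect it costs 5.4 points of power at 10/5 (60.9% to 55.5%). The pooled estimate there has the smaller mean squared error for p below about 2.9 SUV. This stands, and belongs in the stated cost.

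A reader might infer that type I error is well above 5%. That takes a log scale, log-scale SDs and a proportional visit effect, none of which is in the documents, together with accrual of only 13 men. The plan tests raw SUVmean. A reader might also take four men a year for five years (4 × 5 = 20) as a forecast shortfall. It shows no margin, but the accrual rate is stated as approximate and no shortfall is predicted.

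**Conclusion.** The point holds as a minor improvement. As designed, at 10/10, the primary estimate is unbiased and the test errs on the conservative side. The documents do not support a reading that the primary result would be invalid. The loss is about 0.3 points of power at a visit effect of 1 SUV, 1.5 at 2 and 3.4 at 3, and the last is hard to reconcile with a mean of 2.6 if the shift is a uniform drop.

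Bias arises only if the order groups are unequal and a visit effect exists. At p = 2 it is 0.35 SUV at 10/7 and 0.67 at 10/5, against an assumed effect of 6.6. Type I error stays near 5% at those splits and rises noticeably only at about 10/3 or an equally uneven split.

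These figures assume an additive visit effect common to both conditions, normally distributed changes and the plan's own means, SDs and correlation. The size of the visit effect is not in the documents.

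**What to change.** In 11.1, name the order-adjusted analysis as primary: average the change within Group A and within Group B, take the simple average of the two group means, and test it with the pooled within-group SD on 18 df. A mixed model with condition, scan position and a patient effect is equivalent, provided the patient variance is not estimated at zero. If a rank test is used, compare scan 1 minus scan 2 between the two order groups with a Wilcoxon rank-sum test, in which the visit effect cancels. Use the same form for bladder SUVmax, bladder volume and renal SUV. In section 8, state that a replacement takes the withdrawn patient's order.

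The change is to wording only and needs no new data or patients. At 10/10 it costs one degree of freedom (power 74.9% to 74.7% with no visit effect). If the groups end up unequal it costs more: with no visit effect, 67.1% to 65.4% at 10/7 and 60.9% to 55.5% at 10/5. The replacement rule helps to keep that cost small.
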